## k. Limitations and Alternative Strategies

This study has been proposed for only one center but depending on the findings from this study, it will be expanded to other centers in the future. Additional microbiological methods will be limited to serological testing alone, mainly due to budgets limits. Although molecular tests are more sensitive and specific, molecular testing has not been planned for this study because of the budget limits.

This one center study will serve as a pilot study with limited number of patients has been planned because of the budget limit. However, the results of this study will be useful for treatment of febrile patients. Additionally, the results of this study will be useful for designing larger, multi-centered studies in the future.

## 6. PROTECTION OF HUMAN SUBJECTS (ETHICAL CONSIDERATIONS)

This clinical research project will be submitted for a full board approval by the PHAS Institutional Research Committee. Patients will be enrolled from Patan Hospital's inpatient ward after taking informed consent on an informed consent form (ICF) as approved by the PAHS IRC. All patients will be provided written information about the study in Nepali language before enrollment. For patients who

DEFINe Project Principal Investigator: [name]

are unable to understand Nepali, either a family member or a hospital staff will be used as an interpreter to overcome the language barrier and to help the patient understand the study process and its potential harms and benefits.

This project will have equal opportunities for inclusion of women and minorities. Children will be excluded because of a different spectrum of infectious agents outside the scope of this study.

All personal data collected for the study will be stored in a confidential manner in a secure computer with password protection. Only the research team and assigned data analyst will have access to the database. Any new information received during the study will be revealed to the patient. Patients enrolled in the study will be able to withdraw their consent at anytime they wish. Any serious adverse events will be reported to the IRC.

**Registration:** After IRC approval, this study will be registered at Clinical Trial.gov.

#### 7. DATA SAFETY AND MONITORING PLAN

All data entered into the database will be secured and password protected. The study principal investigator and co-investigators will review data from time to time for consistency in data collection. An interim data analysis will be done after enrollment of 25% and 50% of the patients.

Data safety and monitoring will be done by an independent committee known as DSM board consisting of two senior level medical doctors including one internal medicine physician and one microbiologist, and a representative of ethics committee or IRC.

The DSMB will review the interim data and events reports to conclude with their recommendations to whether the study should continue without change, be modified, or be terminated.

#### 8. EXPECTED OUTPUTS (STUDENT TRAINING AND PUBLICATIONS)

This study will help the internal medicine residents and infectious disease fellows at PAHS to learn to design and conduct clinical studies. They will also participate in patient enrollment, data collection, analysis and presentation/publication phases of the study.

The results of this study will be shared within and outside the institution in the form of scientific presentations and publication in peer-reviewed journals.

#### 9. ORGANIZATION OF THE STUDY

Study staff will consist of the followings:

Staff category	Number	Role in study
Principal Investigator	1	Design, Supervision,
		Conduction, Data monitoring,
		Analysis, Write up for

		publication, and Scientific
		presentations
Co-Investigators	2	Design, Enrollment, Data
		collection supervision, Patient
		monitoring, Scientific
		presentation and publication
Researchers (Infectious	2-3	Patient enrollment, consent,
Diseases fellows and Internal		clinical follow up and data
medicine residents)		collection, data entry
Statistician	1	Data analysis

## **10. STUDY TIMELINE**

Events	Details	Timeline
	IRC approval	Jan 2025
Preparatory Phase	Team preparation	Oct-Dec 2024
	Lab setup/supplies	Oct-Dec 2024
	Enrollment (12 months)	1 Feb 2025- 31 Jan 2026
Interventional Phase	Laboratory tests	1 Feb 2025- 31 Jan 2026
interventional Filase	Follow up	1 Feb 2025- 31 Jan 2026
	Data Collection	1 Feb 2025- 31 Jan 2026
Data Analysis and	Statistical analysis	1 Feb 2026- 31 Mar 2026
Reporting Phase	Report and Manuscript preparations	Apr-Jun 2026

# 11. DETAILED BUDGET

Budget Item		Unit Cost (Rs.)	Number	Total Cost (Rs.)
A.	Personnel			
	[name] (10% effort)	129011.	0.10	12,900
	[name] (20% effort)	82074.	0.20	16,414.
	[name] (10% effort)	76867.	0.10	7686.
B.	Equipment, Consumables, Services			
	Serological test by ELISA and/or RDT	500	7x97	339,500
	Other lab supplies for sample			
	collection, processing and	200	97	19,400
	transportation of samples			
C.	Travel/Transportation of sample	NA	NA	NA
D.	Facilities and Administrative			
	Presentation and publication	10,000	1	10,000
	TOTAL =			Rs. 405,900.

#### 12. ASSOCIATION TO NATIONAL PRIORITY

Under the Epidemic and Outbreak Surveillance Programme of Government of Nepal, Ministry of Health and Population (MOHP), the Early Warning and Reporting System (EWARS) has been set up in 81 sites of the country. However, the laboratory testing for various new infectious diseases prevalent in the Southeast region are not available at these sites or in major hospitals of Nepal. This study is expected to identify additional infectious diseases prevalent in Nepal with the laboratory confirmation of the etiologic agents.

Increasing antimicrobial resistance has been identified one of the major causes of morbidity and mortality in hospitals. Therefore, control of antimicrobial resistance has been another national priority. and improve the appropriate use of antimicrobial agents with targeted therapy. The laboratory tests used in this study will help to identify additional infectious diseases. This information will be helpful to the clinicians to design initial empiric antibiotic therapy based on epidemiological and clinical features. A more appropriate choice of antibiotics will decrease the unnecessary use of multiple broad-spectrum antibiotics, which in turn will help to reduce antimicrobial resistance, and improve patient outcome. New information discovered from the study expected to be useful for making policies to prevent and control various infectious diseases such as vector-borne infections and other communicable diseases.

## APPENDIX – 1.

# **DEFINe Study Questionnaire for Database**

## **Screening Questions**

## A. Definition of Acute Undifferentiated Fever (AUF)

Acute undifferentiated fever (AUF) will be defined as a febrile illness with a temperature of 38°C (100.4°F) or higher for at least a duration of 3 days to 21 days, which presents without an obvious cause on the basis of clinical, radiological, and rapidly available laboratory investigations, and not associated with nosocomial infection, neutropenia, or immunosuppressing conditions [10].

No.	Question	Yes	No
a1	Temperature 38C (100.4F) or higher?		
a2	Duration of fever > 3 days and <21 days?		
a3	Cause of fever unknown after routine work up including		
	clinical, radiology and lab evaluations?		
a4	Is it a Nosocomial infection?		
a5	Neutropenia ruled out?		
a6	Immunosuppression present?		
a7	Does the patient meet all criteria for undifferentiated fever?		
	(Needs to answer "Yes" to 1,2&3, and "No" to 4,5,&6)		

If answer to a7 is "Yes", proceed with questions in "b. Inclusion/Exclusion criteria"

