#### 5. APPROACH: STUDY DESIGN AND METHODOLOGY

This will be a randomized, open-label, prospective study which will include patients admitted to the hospital with an undifferentiated febrile illness of 3-days or longer duration. In addition to the history, physical exam and routine laboratory tests and X-ray, when clinically indicated, a battery of laboratory investigations will be performed to identify the etiology of fever.

a. Definition of Acute Undifferentiated Fever (AUF)

Acute undifferentiated fever (AUF) will be defined as a febrile illness with a temperature of 38°C (100.4°F) or higher for at least a duration of 3 days to 21 days, which presents without an obvious cause on the basis of clinical, radiological, and rapidly available laboratory investigations, and not associated with nosocomial infection, neutropenia, or immunosuppressing conditions [12].

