#### b. Study population

This study will be conducted in the inpatient ward of Patan Hospital.

Patients admitted with undifferentiated fever of at least for 3 days to 21 days duration will be enrolled in this study.

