#### c. Inclusion criteria

- 1. Age 16 years or older
- 2. Documented fever (T ≥100.4F or ≥38C) of 3 days to 21 days duration
- No obvious diagnosis found on the basis of clinical, radiological, or initial routine laboratory tests\*
- 4. Admitted to the medical unit of hospital
- 5. Signed ICF (informed consent form)

(\* Initial routine laboratory tests for an etiologic diagnosis of febrile illness work up includeblood and urine cultures, malaria RDT or thick and thin smears, sputum culture and GeneXpert for MTB (if suspected on chest X-ray), and serologies for scrub typhus, dengue, Dengue, Scrub typhus, Leptospirosis, Brucellosis, Kala azar, and HIV, as indicated based on clinical picture)

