#### d. Exclusion criteria

- 1. Fever of less than 3 days or more than 21 days duration
- 2. Outpatients

Principal Investigator: [name]

- 3. Patients being discharged from Emergency Room
- 4. Children (younger than 16 years in age)\*\*
- 5. Immunocompromised patients
- 6. Neutropenia (ANC <500 per cumm)
- 7. Known case of HIV infection
- 8. Admission to a hospital for 48-hours or longer within past 30 days

(\*\*Children under 16 years will be excluded since they have different causes of febrile illnesses requiring a different set of lab tests which is beyond the scope of this study.)

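### Section A of the screening form rejects patients whom the protocol's own criteria accept: the neutropenia item is scored backwards, and the duration item drops days 3 and 21

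*Protocol*

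**What the plan says.** Appendix 1, section A, turns the definition of acute undifferentiated fever into six Yes/No items (a1 to a6) and a summary item, a7. The note under a7 gives the passing pattern: "Needs to answer 'Yes' to 1,2&3, and 'No' to 4,5,&6". The instruction after the table makes a7 a gate to section B: "If answer to a7 is 'Yes', proceed with questions in" the inclusion and exclusion section.

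Two items matter here:

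- a5 asks "Neutropenia ruled out". Its neighbours a4 (nosocomial infection) and a6 (immunosuppression) ask whether a disqualifying state is present.
- a2 asks "Duration of fever > 3 days and <21 days".

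On duration, the rest of the protocol says:

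- Section 5.a, the definition: "for at least a duration of 3 days to 21 days". The same definition is printed above the section A table.
- Section 5.b, study population: "undifferentiated fever of at least for 3 days to 21 days duration".
- Section 5.c, inclusion criterion 2, repeated as b2: "Documented fever (T ≥100.4F or ≥38C) of 3 days to 21 days duration".
- Section 5.d, exclusion criterion 1, repeated as b8: "Fever of less than 3 days or more than 21 days duration".

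On neutropenia, the definition requires that it be absent, and exclusion criterion 6 (repeated as b12) excludes an ANC below 500 per cumm. Section 5.e and the instruction that closes section B make enrolment depend on the inclusion and exclusion criteria.

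**The concern.** The governing criteria agree with each other. Section A comes before them on the form and gives a different answer for patients they accept.

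The a5 problem is one of direction. A patient with a documented adequate neutrophil count answers Yes, the note demands No, and the patient does not reach section B. A complete blood count is part of the standard of care evaluation and baseline ANC is collected (item C11), so literal use would stop most eligible patients. If staff answer a5 by its evident meaning and still mark a7 Yes, each correctly screened patient has a record that breaks the printed rule.

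The a2 problem is quieter. Enrolment would carry on normally while patients at exactly 3 or 21 days were turned away. Aim 1 is a proportion among patients with fever of 3 to 21 days, so the population sampled would be narrower than the one named, and the protocol's lower entry limit is among the values lost.

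**Working it through.** The protocol states no figure to reproduce. The check applies the form's rules literally and compares them with the criteria.

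**Inputs.** From section A: a7 passes if a1, a2 and a3 are Yes and a4, a5 and a6 are No. From sections 5.c and 5.d, and b2, b8 and b12: duration d is accepted if 3 ≤ d ≤ 21, and neutropenia is excluded. From a2: 3 < d < 21.

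**Step 1: the a7 rule.** Six Yes/No items give 2^6 = 64 answer patterns. One passes: Yes, Yes, Yes, No, No, No. In that pattern a5 is No, which means that neutropenia has not been ruled out.

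**Step 2: neutrophil status, with every other item passing (for example, day 4 of fever).**

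| Status | a5 | a7 note | Section B |
|---|---|---|---|
| Ruled out | Yes | fails | would pass, but is not reached |
| Known present | No | passes | stopped at b12 |
| Not established | No | passes | passes |

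The only status that gets through both sections is the one in which nobody has settled the question. Known neutropenia is still caught, so the error is wrongful rejection and not enrolment of patients known to be neutropenic.

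**Step 3: duration.**

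| Days of fever | a2 | b2 and b8 |
|---|---|---|
| 2 | fails | fail |
| 3 | fails | accept |
| 4 | passes | accept |
| 20 | passes | accept |
| 21 | fails | accept |
| 22 | fails | fail |

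In whole days the criteria accept 21 − 3 + 1 = 19 values, and a2 accepts 20 − 4 + 1 = 17. The difference is days 3 and 21. This counts values and not patients; the protocol gives no distribution of fever duration.

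**Step 4: the rules after correction.** With a5 scored so that ruled out is the passing state, and a2 read as 3 ≤ d ≤ 21, an otherwise eligible patient with neutropenia ruled out passes a7 at days 3, 10 and 21, and a patient in whom it is not ruled out fails. Section A then agrees with section B on both points. Correcting a5 alone still fails days 3 and 21, so both changes are needed.

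**The case against.** The strongest reply is that this is a drafting slip with little practical effect. The binding criteria are correct, the definition is printed directly above the table, and a7 itself asks whether the patient meets that definition; the scoring note is only a parenthesis beneath it. A clinician with a normal count in hand would mark a7 Yes. The form also gives no explicit action for a7 = No. Much of this stands. The a5 error would probably be noticed, and the likelier result is an inconsistent record, not a halted trial. But an instruction to proceed on Yes is naturally read as a gate, and section B cannot rescue patients who never reach it.

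On a2, the signs might have been typed as underlined > and < in the source and lost their underline when the PDF was read. The symbol ≥ survives elsewhere in the appendix (b2 and the qSOFA table), but that does not settle how a2 was typed. The text as it stands supports the point, and a glance at the source form would resolve it. The a5 finding does not depend on this.

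Two further cautions are fair. The Sample Size text describes enrolment by a three-day fever, a value that a2 rejects, but this is loose shorthand and carries little weight. The REDCap build is not shown. The appendix is titled as the questionnaire for the database, so carry-over is likely but not certain.

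**Conclusion.** Both contradictions hold on the text as given. Read literally, section A fails all otherwise eligible patients in whom neutropenia has been ruled out, and it fails those at exactly 3 or 21 days of fever. The first conclusion needs only the printed form. The second also assumes that the strict signs in a2 are as printed in the source.

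The consequence is limited. Losses would occur before randomisation, so this alone does not bias the comparisons under aims 2, 3 and 5. The share of patients on the two boundary days is unknown, so the effect on aim 1 cannot be quantified and is probably small. Even so, an eligibility gate that returns the wrong answer should be corrected before use.

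**What to change.** 1. Reword a5 to ask whether neutropenia (ANC below 500 per cumm) is present, so that No is the passing answer and the a7 note can stay. Alternatively, keep a5 as worded and move it to the Yes list in the note. The two differ only when the count is not established: such a patient would be answered No and pass under the first, and would fail under the second. The investigators should choose knowingly.
2. Check a2 against the source form and bring it into line with the inclusive 3 to 21 day range in sections 5.c and 5.d and items b2 and b8.
3. Make the same two changes in the matching REDCap items.

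The cost is two lines of the form and the matching database items. The eligibility criteria, sample size and procedures do not change. If screening has already begun, section A records with a5 = Yes or with a fever duration of exactly 3 or 21 days should be reviewed to see whether anyone was turned away.

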## B. Inclusion/Exclusion criteria

Patients needs to meet al of the following Inclusion Criteria before enrollment:

No.	Question	Yes	No
b1	Age 16 years or older		
b2	Documented fever (T ≥100.4F or ≥38C) of 3 days to 21 days		
	duration		
b3	No obvious diagnosis found on the basis of clinical,		
	radiological, or initial routine laboratory tests*		
b4	Admitted to the medical unit of Patan Hospital		
b5	Informed consent form (ICF) signed		
В6	Patient meets all of the above inclusion criteria		

Page 14

(\* Initial routine laboratory tests for an etiologic diagnosis of febrile illness work up includeblood and urine cultures, malaria RDT or thick and thin smears, sputum culture and GeneXpert for MTB (if suspected on chest X-ray), and serologies for scrub typhus, dengue, Dengue, Scrub typhus, Leptospirosis, Brucellosis, Kala azar, and HIV, as indicated based on clinical picture)

#### Patient should meet none of the Exclusion criteria below:

No.	Question	Yes	No
b7	Children (younger than 16 years in age)**		
b8	Fever of less than 3 days or more than 21 days duration		
b9	Outpatients		
b10	Patients being discharged from Emergency Room		
b11	Immunocompromised patients		
b12	Neutropenia (ANC <500 per cumm)		
b13	Known case of HIV infection		
b14	Hospital admission for 48-hours or longer within past 30 days		
b15	Patient does not meet any of the above exclusion criteria		

(\*\*Children under 16 years will be excluded since they have different causes of febrile illnesses requiring a different set of lab tests which is beyond the scope of this study.)

If patient meets all of Inclusion criteria and none of the exclusions, proceed with patient consent followed by randomization and enrollment.

#### **Randomization Result**

	Information	Remarks
Patient's study ID no.	D001, D002, D003,	
Date of Birth (in AD)	DD/MM/YYYY	
Address (District where patient lives)	District name	
Admission date (in AD)	DD/MM/YYYY	
Unit location	Ward, HDU, ICU	
Randomization Arm	Group A, Group B	

# C. Clinical and Laboratory Questionnaire (Standard of Care Evaluation for all participants)

No.	Questions/ Variables	Data / value	Unit
	BASELINE CLINICAL DATA		
C1	Duration of fever	No. of days	
C2	Clinical Diagnosis		
C3	System involvement	RTI, GI, UTI, CVS, CNS,	
		SSTI, Blood, Sepsis,	
		Lymphatic, Other	
C4	Comorbidities	None, DM, HTN,	
		COPD/chronic	
		pulmonary dis., CHF,	
		MI, PVD, CLD/Liver	
		failure, PUD, CVA,	
		hemiplegia, dementia,	
		CTD, AIDS, solid	
		tumor, lymphoma,	
		leukemia, other	
C5	Temperature in Celsius (baseline at		Celcius
	presentation)		
C6	BP (baseline at presentation)		mmHg
C7	Pulse (baseline at presentation)		per min.
C8	Resp rate (baseline at presentation)		per min.
C9	SaO2 (baseline at presentation)		%
C10	WBC (baseline at presentation)		per cumm
C11	ANC (baseline at presentation)		per cumm
C12	ALC (baseline at presentation)		per cumm
C13	AEC (baseline at presentation)		per cumm
C14	Hgb (baseline at presentation)		g/dL
C15	Plt		per cumm
C16	CRP		
C17	ESR		per hour
C18	Cr		
C19	ALT		
C20	AST		
C21	UA: pus cells		
	MICROBIOLOGICAL DATA		
M1	Blood culture result	Organism name	
M2	Urine culture result	Organism name	
M3	Sputum culture result	Organism name	
M4	Pus culture	Organism name	
M5	GeneXpert	Positive/negative	
M6	Dengue serology	NS1, IgM, IgG	
M7	Scrub typhus	Positive/negative	

M8	Malaria RDT	P falciparum, P vivax,
		other
M9	Kala Azar	Positive/negative
M10	Brucella	Positive/negative
M11	MTB	Positive/negative
M12	Leptospirosis	Positive/negative
M13	Hepatitis A	IgM
M14	Hepatitis E	IgM
M15	Hepatitis B	HBsAg
M16	Hepatitis C	HBC Ab
M17	HIV	
M18	Other test results ()	
M19	Other test results ()	
M20	Other test results ()	
	RADIOLOGICAL DATA	
R1	X-ray finding	Consolidation,
		Infiltrates, Pleural
		effusion, CHF, ARDS,
		other
R2	CT Chest	Consolidation,
		Infiltrates, Pleural
		effusion, CHF, ARDS,
		other
R3	CT Abdomen	Hepatomegaly,
		pancreatitis,
		Cholecystitis, Gall
		stone, Ascites,
		appendicitis, typhlitis,
		intrabdominal
		abscess,
		lymphadenopathy,
		other
R4	USG Abdomen	Hepatomegaly,
		pancreatitis,
		Cholecystitis, Gall
		stone, Ascites,
		appendicitis, typhlitis, intrabdominal
		abscess,
		lymphadenopathy, other
R5	CT/MPI ckull	
KO	CT/MRI skull	Abscess, Meningitis,
		Encephalitis,
		parameningeal focus, other
		otilei

R6	Echocardiogram	Valvular vegetation,
		Pericardial effusion,
		other
	ADDITIONAL SEROLOGICAL EVALUATIONS	Results
	(for Group B patients only)	
D1	Murine typhus	Positive, negative, NA
D2	Bartonella	Positive, negative, NA
D3	Q-fever	Positive, negative, NA
D4	Chikungunya	Positive, negative, NA
D5	Zika	Positive, negative, NA
D6	Japanese B encephalitis	Positive, negative, NA
D7	West Nile virus	Positive, negative, NA

# D. Severity and Comorbidity indices

# i. qSOFA score

Altered mental status GCS <15	Yes	No
Respiratory rate ≥22/min	Yes	No
Systolic BP ≤100 mmHg	Yes	No
Total Score		

# ii. Updated Charlson Comorbidity index score

Index	Score
CHF	2
Chronic pulmonary disease	1
Connective tissue disease	1
Dementia	1
DM with end organ damage	1
Liver disease- Mild	2
Moderate to severe	4
Renal disease- moderate to severe	2
Hemiplegia	2

Tumor without metastasis	2
Tumor with metastasis	6
Leukemia	2
Lymphoma	2
AIDS	2
Total Score	

# E. Antimicrobials Dose and Durations

	Antimicrobial agent used	Route	Total Dose per day (Grams)	Total No. of days used
AM1		PO, IV	grams	No. of days
AM2				
AM3				
AM4				
AM5				
AM6	Appropriateness of Antimicrobials used (to be determined by an independent physician)	Yes, No, Partially		

# F. Outcomes

Outcome variable	Results
Outcome at the end of hospitalization	Discharge- complete recovery,
	Discharge- partial recovery,
	Death
Composite outcome at the end of	Good Outcome (complete plus
hospitalization	partial recovery)
	Poor outcome (Death)
